4.2 Rationale

4.2.1 Rationale Selected Subject Population

Melanoma is the 5th most prevalent cancer in the United States and accounts for approximately 5 percent of all skin cancers. However, melanoma is responsible for 80 percent of all skin cancer related deaths. The median overall survival for patients with metastatic disease is approximately 6-12 months, although this may be shifting with new available systemic therapy. Recent studies with combination T cell checkpoints suggest an enhanced therapeutic response with two drugs although toxicity was also increased [35]. Thus, a high priority has been placed on testing combination immunotherapy regimens and those already demonstrating durable survival should be of the highest priority for clinical investigation.

In 1998 high-dose bolus IL-2 was approved for melanoma and induces objective responses in 15-20% of patients [17]. In 2011, the anti-CTLA-4 monoclonal antibody ipilimumab was approved based on randomized Phase III data demonstrating a survival benefit when compared to peptide vaccine therapy with a response rate of approximately 10% [19]. Two additional checkpoint inhibitors, pembrolizumab and nivolumab have been approved by the U.S. Food and Drug Administration for the treatment of metastatic melanoma since 2014, each with a response rate of approximately 25-40%. As monotherapy, each drug is only effective in a fraction of the treatment population, so better therapeutic strategies, including combinations of 

[REDACTED]

[REDACTED]

[REDACTED]

[REDACTED]

[figure not shown]
[REDACTED]

[REDACTED]

[REDACTED]

[REDACTED]

IL-2 + α PD-1 Combination Immunotherapy

Clinical data with high-dose IL-2 with ipilimumab suggest that combination with a checkpoint inhibitor is safe and effective.

- The combination of IL-2 and ipilimumab has been demonstrated to be tolerable in a Phase I/II study of 36 patients [37]. Most of the patients in this small study received the standard dose of 3 mg/kg ipilimumab in combination with high-dose IL-2. There were expected toxicities related to IL-2 and well as Grade 3 and 4 immune-related adverse events in 14% of patients, which were attributed to ipilimumab. All patients recovered from these toxicities without sequelae.
- At the time of first publication, the overall response rate was 22% (14% partial responses and 8% complete responses). With continued follow-up, patients demonstrated late improvements in their responses. The overall response rate increased to 25%, and most notably, the rate of complete response increased to 17% [38].

- Ongoing clinical trials are investigating high dose IL-2 and ipilimumab concurrently (NCT02203604) and sequentially (NCT01856023). Other trials are investigating tumor-infiltrating lymphocytes with IL-2 and anti-PD-1 sequentially (NCT02500576) and concurrently (NCT01993719).
- Analysis of registry data has documented survival in over 50 patients who were treated with high dose IL-2 following immune checkpoint blockade [39]. According to data collected in the IL-2 observational registry "PROCLAIM", IL-2 given before or after checkpoint inhibitor as standard of care was not associated with increased incidence of severe or unexpected toxicities (*Cytokine Working Group teleconference, unpublished data, manuscript in preparation*).
- IL-2 and pembrolizumab have both individually been demonstrated to be effective in metastatic melanoma and are FDA-approved for this indication. Their side effect profiles are partially overlapping, and given the experience to date combining IL-2 with ipilimumab, which is more toxic than pembrolizumab, the combination of pembrolizumab and IL-2 is expected to be safe and effective.

This trial uses intermittent IV bolus dosing of IL-2 because it is the current standard and the pharmacokinetics are more reliable than subcutaneous administration.

4.2.3 Rationale for Dose Selection of IL-2

This study will test the safety of escalating doses of IL-2 doses that spans two orders of magnitude, starting with a low dose and escalating upwards. The threshold of IL-2 for T-cell activation varies widely among individuals and cell types. Given that biologic phenomena have a threshold effect and do not have a linear and predictable dose-response curve, a high dose of IL-2 may not be required for efficacy. In contrast, low doses of IL-2 have been reported to preferentially expand Tregs and this could limit efficacy. While Treg expansion has generally been associated with suppression of anti-tumor immunity, the full impact of low-dose IL-2, especially when administered in combination with PD-1 blockade, is unknown.

The trial will explore a low dose (6,000 IU/kg) of IL-2 based on preclinical data [36]. Very low dose IL-2 (6,000 IU/kg) is appealing because the toxicity is expected to be lower and it may make combination therapy more generalizable (i.e. outpatient treatment, community settings). There is limited data supporting the efficacy of intermediate-dose (60,000 IU/kg) IL-2 in renal carcinoma [40], but it has not been effective as monotherapy in melanoma. The trial will test high-dose IL-2 (600,000 IU/kg) because this is the most effective and widely used dose. This trial uses intermittent IV bolus dosing of IL-2 because it is the current standard and the pharmacokinetics are more reliable than subcutaneous administration.

4.2.4 Rationale for Dose Selection of Pembrolizumab

A flat dose of pembrolizumab will be administered with IL-2 in doses ranging up to high-dose IL-2 at 600,000 IU/kg, which is the FDA-approved dose.

An open-label Phase I trial (Protocol 001) was conducted to evaluate the safety and clinical activity of single agent MK-3475. The dose escalation portion of this trial evaluated three dose levels, 1 mg/kg, 3 mg/kg, and 10 mg/kg, administered every 2 weeks (Q2W) in subjects with advanced solid tumors. All three dose levels were well tolerated and no dose-limiting toxicities were observed. This first in human study of MK-3475 showed evidence of target engagement and objective evidence of tumor size reduction at all dose levels (1 mg/kg, 3 mg/kg and 10 mg/kg Q2W). No MTD has been identified to date. Recent data from other clinical studies within the MK-3475 program has shown that a lower dose of MK-3475 and a less frequent schedule is sufficient for target engagement and clinical activity.

PK data analysis of MK-3475 administered Q2W and Q3W showed slow systemic clearance, limited volume of distribution, and a long half-life (refer to IB). Pharmacodynamic data (IL-2 release assay) suggested that peripheral target engagement is durable (>21 days). This early PK and pharmacodynamic data provided scientific rationale for testing a Q2W and Q3W dosing schedule.

A population pharmacokinetic analysis has been performed using serum concentration time data from 476 patients. Within the resulting population PK model, clearance and volume parameters of MK-3475 were found to be dependent on body weight. The relationship between clearance and body weight, with an allometric exponent of 0.59, is within the range observed for other antibodies and would support both body weight normalized dosing or a fixed dose across all body weights. MK-3475 has been found to have a wide therapeutic range based on the melanoma indication.

The differences in exposure for a 200 mg fixed dose regimen relative to a 2 mg/kg Q3W body weight based regimen are anticipated to remain well within the established exposure margins of 0.5 – 5.0 for MK-3475 in the melanoma indication. The exposure margins are based on the notion of similar efficacy and safety in melanoma at 10 mg/kg Q3W vs. the dose regimen of 2 mg/kg Q3W (i.e. 5-fold higher dose and exposure). The population PK evaluation revealed that there was no significant impact of tumor burden on exposure. In addition, exposure was similar between the NSCLC and melanoma indications. Therefore, there are no anticipated changes in exposure between different indication settings.

The choice of the 200 mg Q3W as an appropriate dose for fixed dosing is based on simulations performed using the population PK model of pembrolizumab showing that the fixed dose of 200 mg every 3 [REDACTED]

with those obtained with the 2 mg/kg dose every 3 weeks, 2) will maintain individual patient exposures in the exposure range established in melanoma as associated with maximal efficacy response and 3) will maintain individual patients exposure in the exposure range established in melanoma that are well tolerated and safe.

A fixed dose regimen will simplify the dosing regimen to be more convenient for physicians and to reduce potential for dosing errors. A fixed dosing scheme will also reduce complexity in the logistical chain at treatment facilities and reduce wastage.

4.2.5 Rationale for Efficacy Endpoints

The primary endpoint is the best objective response rate (BORR) by RECIST v1.1 with a confirmatory scan, as indicated. Radiographic response to therapy has been a reliable surrogate endpoint in the high-dose IL-2 literature, as patients who have complete and partial responses have improved overall survival on average compared with those who have stable or progressive disease. The use of BORR as a surrogate endpoint decreases the length of the trial and provides sufficient evidence of activity of the combination of drugs. In addition, landmark analysis of progression-free and overall survival will be determined as these are also valid endpoints in this population.

4.2.6 Rationale for Biomarker Endpoints

4.2.6.1 Peripheral Blood

Given the high short-term toxicity of IL-2 and the low frequency of responses, various parameters in the blood have been explored as predictive biomarkers. High serum VEGF, fibronectin [28], and CRP [41] have been negatively correlated with clinical responses to IL-2. Select blood proteins as well as cytokine profiles will be examined in this study. On-treatment effects such as increases in the effector T cell/regulatory T cell ratio, and decreases in amount of circulating regulatory T cells have been previously reported to correlate with therapeutic activity and will be explored in this study as well.

4.2.6.2 Tumor Microenvironment

It is hypothesized that the combination of pembrolizumab and IL-2 will induce tumor-specific immunity, and lead to long-term T cell memory and inhibition of CD4+CD25+ regulatory T cells in the tumor microenvironment, as well as increased infiltrates of effector CD8+ and NK lymphocytes into the tumor. Further, elevated levels of tumor-associated PD-L1 expression have been correlated with better clinical responses to PD-1 blockade therapy. Therefore, expression of PD-L1 and PD-L2 will be assayed (QualTek Laboratories assay). The immune cells in the tumor microenvironment will be phenotyped and quantified using flow cytometry. Tumor DNA and

RNA will be probed for general mutation load and for defined mutations, such as NRAS, particular single nucleotide polymorphisms, INF gamma pathway signature genes using NanoString profiling [42].

5.0 METHODOLOGY

5.1 Entry Criteria

5.1.1 Diagnosis/Condition for Entry into the Trial

Histologic or cytologic diagnosis of cutaneous melanoma, mucosal melanoma or melanoma of unknown primary.

5.1.2 Subject Inclusion Criteria

In order to be eligible for participation in this trial, the subject must:

1. Histologic or cytologic diagnosis of cutaneous melanoma, mucosal melanoma, or melanoma of unknown primary that is considered unresectable (Stage III) or metastatic (Stage IV).
2. Be willing and able to provide written informed consent/assent for the trial.
3. Be ≥ 15 years of age on day of signing informed consent.
4. Have measurable disease evident on radiographs (preferred) or clinical examination. For this protocol, measurable disease is defined as at least one evaluable tumor that is at least 10 mm in longest dimension.
5. Have a performance status of 0 or 1 on the ECOG Performance Scale (See Appendix 11.1 for classification criteria).
6. Patients must have a brain MRI or CT (with and without contrast) that is free of active metastases. Metastases that have been treated with radiation or surgical resection, are stable for at least 4 weeks and do not require steroids are eligible.
7. Normal cardiac function. Patients who have a history of heart disease, or who are over the age of 50 years must have a normal cardiac stress test within the prior 90 days.

8. Normal lung function. Patients who have extensive pulmonary metastases or any chronic pulmonary disease history must have pulmonary function testing demonstrating FEV1 and FVC > 65% of predicted values.
9. Demonstrate adequate organ function as defined in Table 1,

Table 1. Adequate Organ Function Laboratory Values

System	Laboratory Value
Hematological	
Absolute neutrophil count (ANC)	≥1,500 /mcl
Platelets	≥100,000 / mcl
Hemoglobin	≥9 g/dL or ≥5.6 mmol/L without transfusion or EPO dependency (within 7 days of assessment)
Renal	
Serum creatinine OR Measured or calculated* creatinine clearance (GFR can also be used in place of creatinine or CrCl)	≤1.5 X upper limit of normal (ULN) OR ≥60 mL/min for subject with creatinine levels > 1.5 X institutional ULN
Hepatic	
Serum total bilirubin	≤ 1.5 X ULN OR Direct bilirubin ≤ ULN for subjects with total bilirubin levels > 1.5 ULN. Patients with Gilbert's Syndrome must have a total bilirubin < 3.0 mg/dL.
AST (SGOT) and ALT (SGPT)	≤ 2.5 X ULN OR ≤ 5 X ULN for subjects with liver metastases
Albumin	>2.5 mg/dL
Coagulation	
International Normalized Ratio (INR) or Prothrombin Time (PT)	≤1.5 X ULN unless subject is receiving anticoagulant therapy as long as PT or PTT is within therapeutic range of intended use of anticoagulants
Activated Partial Thromboplastin Time (aPTT)	≤1.5 X ULN unless subject is receiving anticoagulant therapy as long as PT or PTT is within therapeutic range of intended use of anticoagulants

*Creatinine clearance should be calculated per institutional standard.

10. Female subject of childbearing potential should have a negative urine or serum pregnancy test. If the urine test is positive or cannot be confirmed as negative, a serum pregnancy test will be required.

11. Female subjects of childbearing potential must be willing to use 2 methods of birth control or be surgically sterile, or abstain from heterosexual activity for the course of the study through 120 days after the last dose of study medication. Subjects of childbearing potential are those who have not been surgically sterilized or have not been free from menses for > 1 year.
12. Male subjects should agree to use an adequate method of contraception starting with the first dose of study therapy through 120 days after the last dose of study therapy.
13. Subject meets institutional requirements for IL-2 therapy.

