11.3.1 Measurable Disease

Measurable lesions are defined as those that can be accurately measured in at least one dimension (longest diameter to be recorded) as ≥ 20 mm by chest x-ray, as ≥ 10 mm with CT scan, or ≥ 10 mm with calipers by clinical exam. All tumor measurements must be recorded in millimeters.

NOTE: Tumor lesions that are situated in a previously irradiated area are not considered measurable.

NOTE: Malignant Lymph Nodes. To be considered pathologically enlarged and measurable, a lymph node must be ≥ 15 mm in short axis when assessed by CT scan (CT scan slice thickness recommended to be no greater than 5 mm). At baseline and in follow-up, only the short axis will be measured and followed.

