11.3.3 Target Lesions

All measurable lesions up to a maximum of 2 lesions per organ and 5 lesions in total, representative of all involved organs, should be identified as **target lesions** and recorded and measured at baseline. Target lesions should be selected on the basis of their size (lesions with the longest diameter), be representative of all involved organs, but in addition should be those that lend themselves to reproducible repeated measurements. It may be the case that, on occasion, the largest lesion does not lend itself to reproducible measurement in which circumstance the next largest lesion which can be measured reproducibly should be selected.

A sum of the diameters (longest for non-nodal lesions, short axis for nodal lesions) for all target lesions will be calculated and reported as the baseline sum diameters. If lymph nodes are to be included in the sum, then only the short axis is added into the sum. The baseline sum of the diameters will be used as reference to further characterize any objective tumor regression in the measurable dimension of the disease.

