11.3.4 Non-target Lesions

All other lesions (or sites of disease) including any measurable lesions over and above the 5 target lesions should be identified as **non-target lesions** and should also be recorded at baseline. Measurements of these lesions are not required, but the presence or absence of unequivocal progression of each should be noted throughout follow-up.

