11.3.5 Evaluation of Target Lesions

Complete Response (CR)	Disappearance of all target lesions. Any pathological lymph nodes (whether target or non-target) must have reduction in short axis to < 10 mm.
Partial Response (PR)	At least a 30% decrease in the sum of the diameters of target lesions, taking as reference the baseline sum diameters
Progressive Disease (PD)	At least a 20% increase in the sum of the diameters of target lesions, taking as reference the smallest sum on study (this includes the baseline sum if that is the smallest on study). In addition to the relative increase of 20%, the sum must also demonstrate an absolute increase of at least 5 mm. Note: the appearance of one or more unequivocal new lesions is also considered progression.
Stable Disease (SD)	Neither sufficient shrinkage to qualify for PR nor sufficient increase to qualify for PD, taking as reference the smallest sum diameters while on study.

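### Inclusion criterion 4 contradicts Appendix 11.3.1 on measurable lymph nodes, so response scoring is unsettled for patients whose only disease is small nodes

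*SAP*

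**What the plan says.** **Entry.** Criterion 4 in section 5.1.2 of the SAP document, with the same sentence in the synopsis, states: "For this protocol, measurable disease is defined as at least one evaluable tumor that is at least 10 mm in longest dimension". The measure is the longest dimension, whatever the type of lesion.

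**Response assessment.** Appendix 11.3.1 (combined protocol and SAP) uses the short axis for nodes: "a lymph node must be ≥ 15 mm in short axis when assessed by CT scan". It also states: "Tumor lesions that are situated in a previously irradiated area are not considered measurable". Appendix 11.3.2 classes everything that falls short as non-measurable.

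**From measurability to scoring.**
- Target lesions are drawn from measurable lesions only (11.3.3): "All measurable lesions up to a maximum of 2 lesions per organ and 5 lesions in total".
- For nodes, the short axis is what counts (11.3.3): "If lymph nodes are to be included in the sum, then only the short axis is added into the sum".
- The rest go elsewhere (11.3.4): "All other lesions (or sites of disease) including any measurable lesions over and above the 5 target lesions should be identified as" non-target lesions.
- PR (11.3.5) is "At least a 30% decrease in the sum of the diameters of target lesions, taking as reference the baseline sum diameters".
- The nodal condition for CR (11.3.5) is "Any pathological lymph nodes (whether target or non-target) must have reduction in short axis to < 10 mm".

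The opening of Appendix 11.3 says that RECIST 1.1 is used with a single modification, which concerns confirmation of progression. It refers to the published RECIST paper for full details.

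**The concern.** Eligibility and response assessment should use one definition of measurable disease, so that everyone who enters can be scored. Here they differ for nodes that are at least 10 mm long but under 15 mm in short axis. A patient with only such nodes can be enrolled, and the text does not say which definition then governs.

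The primary endpoint is BORR by RECIST 1.1. The synopsis also makes a complete response rate above 20% a separate route to calling the approach worth further study. Both depend on how these patients are classified. Section 5.2.2.5 uses response categories when it describes further IL-2 courses, so an undefined category also affects conduct. Such patients could plausibly enrol: unresectable Stage III disease is eligible, and a planned subgroup is metastases limited to skin, lymph nodes and lungs.

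**Working it through.** The plan gives no figure to reproduce on this point. The check applies the two definitions to example nodes and then follows each through the scoring rules.

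**Step 1. Do the definitions disagree?** Inputs: longest dimension ≥ 10 mm (criterion 4); short axis ≥ 15 mm (11.3.1).

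| Node, longest × short axis (mm) | Criterion 4 | 11.3.1 |
|---|---|---|
| 12 × 8 | measurable | not measurable |
| 14 × 12 | measurable | not measurable |
| 18 × 14 | measurable | not measurable |
| 18 × 15 | measurable | measurable |

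For lesions that are neither nodal nor irradiated and are measured by CT or calipers, both rules use 10 mm and agree.

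**Step 2. Suppose 11.3.1 governs.** Take a patient whose only disease is an 18 × 12 mm node.
- The node is not measurable, so it is a non-target lesion and the patient has no target lesion.
- PR is defined only on the sum of target-lesion diameters, so it cannot be reached.
- The 11.3.8 table has 9 rows. Five give CR, PR or SD, and each needs a target-lesion status of CR, PR or SD. One gives NE, for target lesions not all evaluated. Three give PD, and two of these accept any target status.
- Only those two PD rows can fit this patient. Appendix 11.3.6 defines a non-target CR, but no row turns it into an overall response when there is no target lesion.

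**Step 3. Suppose criterion 4 governs.** The node becomes a target lesion and its short axis S enters the sum. For a patient with a **single** node:
- PR point = 0.7 × S
- shrinkage at which the short axis comes down to the 10 mm CR limit = 1 − 10/S

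| S (mm) | PR point (mm) | Shrinkage to 10 mm |
|---|---|---|
| 11 | 7.7 | 9.1% |
| 12 | 8.4 | 16.7% |
| 13 | 9.1 | 23.1% |
| 14 | 9.8 | 28.6% |
| 15 | 10.5 | 33.3% |

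The two thresholds cross where 0.7 × S = 10, that is S = 10/0.7 = 14.3 mm. Below this, the nodal CR limit is reached before a 30% fall, so a single node has no separate PR range. At the 11.3.1 floor of 15 mm the usual order returns: PR at 10.5 mm, then the CR limit at 10 mm. A 12 × 8 mm node is under 10 mm in short axis before treatment starts.

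**Step 4. Does step 3 extend to several nodes?** Not in general. Two nodes of 14 mm sum to 28 mm, so PR needs 0.7 × 28 = 19.6 mm or less. Shrinkage to 8 mm and 11 mm gives 19 mm, a fall of 9/28 = 32.1%. That is PR and not CR, because one node is still at least 10 mm.

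**The case against.** **The override reading.** Criterion 4 presents itself as a protocol-specific definition, so it could be read as overriding the appendix. The node would then be a target lesion and the table would apply. This stands as a possible reading, so the missing table row cannot be stated as fact. It does not make the text sound: the appendix declares a different single modification, and step 3 shows that the nodal CR limit then comes too early for a small single node.

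**Text that could not be read.** Sections 7.1.3 (tumor assessment), 8.4.1 (evaluable for response) and 8.6 (analysis of the primary objectives) are listed in the contents, but their bodies are not in the text available. A figure is missing just before the 11.3.8 table, and the RECIST paper is cited for details. Any of these may hold a rule for patients without target lesions. That limits confidence in the scoring consequence. It does not remove the conflict between criterion 4 and 11.3.1.

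**The word evaluable.** Criterion 4 requires the tumor to be evaluable, which the available text does not define. It might already exclude irradiated lesions or some small nodes. For this reason the further mismatches, on irradiated lesions and on the 20 mm chest x-ray threshold in 11.3.1, are noted as less certain.

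**A stronger inference to avoid.** A reader might conclude that BORR is biased in a known direction, or that these patients both lose PR and inflate the CR rate. The documents do not support this. Losing PR belongs to the reading in which 11.3.1 governs, where the table gives no route to CR. An easy CR belongs to the reading in which criterion 4 governs, where PR can still occur with several nodes.

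**Conclusion.** Criterion 4 and its synopsis copy contradict Appendix 11.3.1 for lymph nodes. Confidence in that is high, since it rests only on the current wording.

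The affected group is patients whose only disease is nodes at least 10 mm long and under 15 mm in short axis. Their number is not given, so neither the size nor the direction of any effect on BORR can be stated.

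The consequence depends on the reading. If 11.3.1 governs, PR is out of reach and the available table offers only PD. If criterion 4 governs, a single node below 14.3 mm in short axis meets the nodal CR size before the PR threshold, and one below 10 mm meets it at baseline. Such patients could then count too easily towards the complete-response criterion. Confidence in these consequences is moderate, because 7.1.3, 8.4.1 or the RECIST paper may add a rule.

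If 8.4.1 makes such patients non-evaluable, they draw on a small allowance: 62 − 60 = 2 to 65 − 60 = 5 patients. The point should be fixed because the primary endpoint depends on it and the change is small.

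**What to change.** Replace the second sentence of criterion 4 in section 5.1.2, and its copy in the synopsis, with: *For this protocol, measurable disease is at least one lesion that is measurable as defined in Appendix 11.3.1.* Every enrolled patient then has at least one target lesion and can be scored with the 11.3.8 table.

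The cost is one sentence in two places, and a few patients with only small nodal disease, or only irradiated lesions, become ineligible. If the sponsor wants to keep those patients, the alternative is to state which definition governs and add a rule for overall response when there is no target lesion. That takes more text. If criterion 4 were chosen to govern, the CR limit for small nodes would also have to be addressed.
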